#### **5.2.2    Post-Treatment Surveillance**

NCCN guidelines will be followed. Surveillance will be every 3-6 month for 2 years then annually thereafter and will include:

- History and Physical
- CA 19-9 Levels
- CT or MRI imaging with IV contrast

## **6.        ADVERSE EVENTS**

### **6.1      Definition of Adverse Event**

An adverse event is any symptom, sign, illness, or experience which develops or worsens during the course of the study, whether or not the event is considered related to the study intervention.

The investigator will be responsible for assessing the etiology of any adverse events and determining if these can be considered a treatment related adverse event (TRAE) which arose directly or indirectly as a result of SBRT. Adverse events will be graded according to the NCI CTCAE Version 4.0. TRAE will be considered “acute” if they occur within 1-4 weeks post SBRT and prior to surgical resection and “late” if they occur after this time period.

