### **2.2 Primary Objectives**

- a) To evaluate the feasibility and tolerability of short course preoperative stereotactic body radiation therapy for resectable pancreas cancer
- b) To determine the rate of Grade 2 or greater acute toxicity of neoadjuvant stereotactic body radiation therapy
- c) To determine intraoperative and postoperative surgical morbidity following neoadjuvant treatment including the amount of fibrosis and total operative time.

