## 6.3 Documentation of Adverse Events

All adverse events, whether observed by the Investigator, elicited from or volunteered by the subject, will be documented. Each adverse event will include a brief description of the experience, the date of onset, the date of resolution, the duration and type of experience, the severity, and the relationship to SBRT, contributing factors, and any action taken with respect to the planned radiation therapy. In addition, any toxicity leading to radiation treatment break and delay in surgical resection beyond 3 weeks post SBRT will be noted.

All patients are expected to undergo surgical resection within 3 weeks after radiation therapy. Any Intraoperative complications including blood loss, total operative time and amount of fibrosis noted by the surgeon will be recorded in the operative report. Post-operative complications including delayed wound healing, blood loss, infection, length of hospital stay, incidence of pancreatic leak, hospital readmissions for complications will also be recorded. Appendix A lists the data the surgical oncology team is responsible for recording.

Treatment related late complications including but not limited to duodenal and intestinal ulceration, perforation, gastritis, bowel adhesions and obstruction, will be recorded at follow ups up to 5 years after treatment.

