## **9. DATA ANALYSIS AND MONITORING**

The purpose of this pilot study is to determine feasibility of preoperative SBRT followed by surgical resection at URMC and to determine its safety and tolerability in a small population of patients. For this phase 1 trial, we plan to enroll 18 patients over 1-2 years with a goal of 12 evaluable cases. This is a generally accepted number of patients for phase 1 trials and will minimize the risks to patients in case the treatment is found to be unsafe. We will stop recruitment and analyze the safety data if there appears to be any grade 3 or greater toxicity on any subject that can be directly attributed to SBRT or if any patients are made ineligible for surgical resection solely due to toxicities from SBRT.

In the case where any patient becomes ineligible for resection due solely to toxicity from SBRT, the study will be immediately closed to accrual. We will stop recruitment and any patient who has not started radiation therapy will have their planned radiation treatment canceled. A patient who has started radiation therapy will undergo an individual discussion with [name] about the risks and benefits of continued treatment.

If a patient experiences grade 3 or greater toxicity directly attributable to SBRT that is reversible and ultimately able to undergo resection, we will analyze the event and attempt to prevent/reduce the adverse event from taking place again. We will discuss the risks and benefits of continued recruitment into the study with our co-investigators and determine whether or not to continue the study. If we believe that modifications can be made that will reasonably reduce the risk of a future event from occurring, we will continue recruitment to the study.

The investigators plan to evaluate the rates of acute toxicity after 12 patients have been enrolled and undergone SBRT and surgical resection. Long term safety and efficacy will be evaluated after all 12 patients have undergone surgical resection and have either been followed for at least 6 month or have died. The primary investigator, [name] will have access to all of the study data.

The Cancer Center Data & Safety Monitoring Committee will monitor the study for safety. Study

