#### DATA SUMMARY:

1. ENROLLMENT			
Since last Report:	_____	Total to Date:	_____
Comments:			

2. ADVERSE EVENTS			
	Serious / Related / Unexpected  :	Other Serious  :	Non-Serious:
Since Last Report:			
Total:			
Comments:			

Serious, possibly/probably/definitely related events that are considered unexpected require prompt reporting to RSRB and DSMC.

Serious events which are unrelated and/or expected require reporting to the RSRB at least annually and to the DSMC per DSMC reporting requirements.

3. SUBJECT WITHDRAWALS				
	Investigator- initiated:	Reason(s):	Subject- initiated:	Reason(s):
Since last report:				
Total:				

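### The primary acute toxicity rate appears to depend on the investigator's attribution with no all-cause rate planned beside it, and the recruitment pause uses a narrower attribution test than the definition of a treatment-related event

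*Combined protocol and SAP*

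**What the plan says.** The relevant text is spread over several sections of the combined protocol and SAP.

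- **Section 2.2, objective (b):** "To determine the rate of Grade 2 or greater acute toxicity of neoadjuvant stereotactic body radiation therapy". No attribution rule is given.
- **Section 6.1:** the investigator assesses the cause of each event and decides whether it is a "treatment related adverse event (TRAE) which arose directly or indirectly as a result of SBRT". Such events are acute "if they occur within 1-4 weeks post SBRT and prior to surgical resection", and late afterwards. Acute is not defined for any other kind of event.
- **Section 6.3:** "All adverse events, whether observed by the Investigator, elicited from or volunteered by the subject, will be documented". The record for each event includes its onset date, severity and relationship to SBRT.
- **Section 6.5:** SBRT is stopped for a patient who has any serious adverse event, or any treatment-related toxicity of grade 3 or higher.
- **Section 9:** recruitment stops for a safety analysis on "any grade 3 or greater toxicity on any subject that can be directly attributed to SBRT". A separate rule covers loss of resection: "In the case where any patient becomes ineligible for resection due solely to toxicity from SBRT, the study will be immediately closed to accrual".
- **Section 9, analysis:** a descriptive report of acute and late toxicity, including surgical morbidity. No all-cause toxicity rate is named.
- **Appendix C, footnote 1:** for reporting, "Serious, possibly/probably/definitely related events that are considered unexpected require prompt reporting to RSRB and DSMC".

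**The concern.** There are two linked problems.

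The first concerns the primary rate. If objective (b) counts only related events, the numerator depends on a causal judgement made without blinding, without a comparator and without written causality criteria. Section 6.5 expects mainly nausea, fatigue and loose bowel movements. That these are hard to separate from the effects of the tumour or a bile stent is a clinical assumption and is not stated in the documents. If it holds, two careful investigators could report different rates from the same patients, and a reader of the published rate could not tell how much rests on attribution.

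The second concerns the link between the patient-level and study-level safety rules. The definition in Section 6.1 takes in indirect effects of SBRT. The recruitment pause in Section 9 is limited to direct ones. The same event can therefore be enough to end one patient's radiation and yet not be enough, on the wording, to start the study-level safety analysis.

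**Working it through.** **Is objective (b) a related-only rate?** Section 2.2 asks for acute toxicity of SBRT. Section 6.1 gives acute a meaning only for treatment-related events, and the investigator decides which those are. No other text supplies an acute window for unattributed events. Related-only is the natural reading, but it is an inference.

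**How far can attribution move the rate?** The plan gives no target rate, threshold, alpha or power. It justifies 12 evaluable patients by convention, so there is no stated figure to reproduce. The denominator used here is the 12 evaluable patients of Section 9.

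One patient is 1/12 = 8.3 percentage points. The exact (Clopper-Pearson) 95% limits for x of n are:

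- lower = Beta quantile at 0.025 with parameters x and n − x + 1
- upper = Beta quantile at 0.975 with parameters x + 1 and n − x

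| Affected patients | Rate | Exact 95% CI |
|---|---|---|
| 4/12 | 33.3% | 9.9 to 65.1% |
| 3/12 | 25.0% | 5.5 to 57.2% |
| 2/12 | 16.7% | 2.1 to 48.4% |

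The move from 4 affected patients to 2 is an illustration; the documents give no such counts. It halves the point estimate.

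**Do the patient-level and study-level rules match?** Take an event of grade 3, not serious, judged by the investigator to be an indirect result of SBRT.

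1. Section 6.1: it is treatment-related, because indirect effects are included.
2. Section 6.5: it is treatment-related and of grade 3, so that patient's remaining SBRT is stopped.
3. Section 9: it is not directly attributed to SBRT, so the pause and safety analysis do not apply on the wording.

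**How sensitive is the pause to that judgement?** Let p be the true chance per patient of a grade 3 or greater event, and q the chance that such an event is called directly attributable. With independent patients, the chance of at least one triggering event in 12 is 1 − (1 − pq)^12.

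| p | q = 1 | q = 0.5 |
|---|---|---|
| 10% (assumed) | 1 − 0.90^12 = 72% | 1 − 0.95^12 = 46% |
| 4/15 = 26.7% | 1 − (11/15)^12 = 98% | 1 − (13/15)^12 = 82% |

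The 4/15 is the acute grade 3 count that Section 1 reports for the proton study, which used a different treatment, so it serves only as a reference value. Both values of q are assumptions.

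**The case against.** The strongest replies are these.

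- **All-cause data are in use.** A reader might infer from the missing all-cause rate that these data are ignored. The documents do not support that. All events are recorded (Section 6.3). The adverse event spreadsheet goes to the monitoring committee with each quarterly report, and unrelated unexpected serious events are reviewed (Section 9). Any serious event, whatever its cause, stops that patient's SBRT (Section 6.5). The surgical morbidity items for objective (c) carry no attribution condition, apart from whether wound healing was worse than usual (Section 6.3 and Appendix A). What remains is narrower: no all-cause toxicity rate is planned for the report, and the Section 9 triggers do not use all-cause events.
- **The attribution wordings do different jobs.** A reader might count four inconsistent definitions of one quantity. In fact the test of sole cause governs closure to accrual and can be read as a stricter tier for a more drastic step. The Appendix C scale governs reporting and defines neither the rate nor a trigger. The mismatch that stands is between the Section 6.1 definition, as applied in Section 6.5, and the grade 3 pause in Section 9.
- **Bias toward tolerability is not shown.** The Section 6.1 wording is inclusive, which favours counting, and an adverse event must develop or worsen during the study, so stable earlier symptoms do not qualify. Error in that direction is a risk only.
- **An all-cause rate answers another question.** Without a comparator it mixes in events from the disease and from stents, and no decision in the plan hangs on the grade 2 rate. This is correct. It is why the all-cause rate should stand beside the attributed rate and not replace it.

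**Conclusion.** The point holds in two parts. First, objective (b) does not say which attribution applies. Its natural reading is a related-only rate decided by the investigator, with no all-cause rate planned alongside. At 12 evaluable patients each changed call is worth 8.3 points, and the assumed change from 4 to 2 affected patients takes the rate from 33% to 17%. Both intervals are wide and overlap heavily, so attribution adds to an estimate that is already imprecise. Second, read literally, an indirect grade 3 event stops a patient's SBRT without pausing recruitment. If half of such events were called not direct, and the true rate were 10%, the chance of a pause in 12 patients would be 46% and not 72%. Both figures rest on assumed inputs.

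A reader might go further and conclude that a single attribution scale must be imposed throughout. The documents do not support that step: it would change when the study pauses or closes, which is for the sponsor to settle. The change is worth making before analysis because it is cheap and bears on a primary objective. Nothing here shows that the reported rate will be wrong.

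**What to change.** 1. State in Section 2.2 or Section 9 whether objective (b) counts treatment-related events only, and by which wording.
2. Add to the planned analysis the proportions of patients with a grade 2 or greater, and with a grade 3 or greater, adverse event before surgery regardless of attribution. Show the attributed proportions beside them, over the same stated window and the same denominator, each with an exact 95% CI.
3. Ask the sponsor to reconcile the attribution wording in Sections 6.1, 6.5 and 9, so that it is clear whether an event judged indirect is meant to reach study-level review. No particular stopping rule is proposed here.

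The cost is one extra table from data that Section 6.3 already requires, plus wording edits. No new data collection or extra reviewer is needed. Over the same window and denominator the all-cause rate cannot be lower than the attributed one, so it will tend to look less favourable, and the report should say that it includes events due to the disease and to stents.

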#### 4.3.3 Surgery

Surgery will be performed no more than 3 weeks after completion of radiation therapy. A pancreaticoduodenectomy (Whipple procedure) with standard lymphadenectomy will be done. Restaging is not required prior to surgery. However if re-staging scans are obtained and demonstrate metastatic disease, surgery will not be performed.

An attempted resection may also be aborted when more advanced or metastatic disease is found at the time of laparotomy. If surgical resection cannot be completed due to the presence of advanced disease, the patient will be withdrawn from the protocol at that time and will continue their care with standard treatment and follow up based on their clinical characteristic.

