## 6.2 Evaluation of Adverse Events

Patients will be assessed for treatment related adverse events weekly during on treatment visit during radiation therapy, at the pre-operative evaluation visit and at follow up visits for at least 5 years. Additional patient visits may be needed as clinically indicated. At these visits, study staff will assess adverse events by recording all voluntary complaints of the subject and by assessment of clinical, radiologic and laboratory features as indicated by the schedule in Appendix B and as clinically warranted. At each study visit, the subject should be questioned directly regarding the occurrence of any adverse experience since his/her last visit.

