## 6.5 Treatment Modification due to adverse events

We do not anticipate any serious treatment related adverse events will take place during or immediately following SBRT treatment. We expect that the most common acute toxicities of radiation therapy will be mild nausea, fatigue and loose bowel movements.

Patients will finish planned radiation if they experience up to grade 2 treatment related toxicity. If patients develop any serious adverse event or any grade 3 or higher treatment related toxicity, SBRT radiation will be stopped and the patients will proceed directly to surgical resection if deemed appropriate by surgical oncology.

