## 7.2 Risks of Participation

- a) Preoperative SBRT could cause toxicities that could delay or even prevent surgical resection which is the most important treatment for resectable pancreatic cancer. However, previous studies have demonstrated that the vast majority of patients who undergo preoperative radiation can safely undergo surgery in a timely fashion.
- b) Radiation therapy can cause both acute and delayed side effects. Acute side effects that take place during or immediately after treatment can include fatigue, nausea, vomiting, diarrhea, loss of appetite and weight loss. These effects are expected to be uncommon and can be managed with supportive care such as anti-nausea or anti-diarrheal medicines. Delayed side effects can take place months to years after radiation and can include delayed wound healing, scar tissue formation and bowel obstruction and structuring. These effects are expected to be very rare. These effects are expected to be similar or decreased compared with the toxicities associated with conventional radiation.
- c) There is a risk of invasion of patient privacy. All the information gathered from patient chart or records, including name and any other identifying information will be strictly confidential and will be kept under lock and key. The patients will not be identified nor will any information that would make it possible for anyone to identify the patient be used in any presentation or written reports about this study. Only summarized data will be presented at meetings or in any publications.

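### Section 6.1 opens the acute window only after SBRT is complete, so a Grade 2+ event confined to the course is neither acute nor late and the primary rate may be understated

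*Combined protocol and SAP*

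**What the plan says.** Section 2.2(b) sets as a primary objective: "To determine the rate of Grade 2 or greater acute toxicity of neoadjuvant stereotactic body radiation therapy". The word acute is given an operational meaning only in section 6.1, where treatment-related adverse events (TRAE) are acute "if they occur within 1-4 weeks post SBRT and prior to surgical resection and" are late if they come after that period.

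Other sections bear on the same period:

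- Section 7.2(b): "Acute side effects that take place during or immediately after treatment can include fatigue, nausea, vomiting, diarrhea" and other effects.
- Section 6.2: TRAE are assessed "weekly during on treatment visit during radiation therapy, at the pre-operative evaluation visit and at follow up visits".
- Section 6.5: "We expect that the most common acute toxicities of radiation therapy will be mild nausea, fatigue and loose bowel movements". It also has rules for toxicity that arises while radiation is being given.
- Section 9: acute toxicity rates are to be evaluated once 12 patients have had SBRT and resection, and acute and late toxicity are to be published descriptively.

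**The concern.** A primary endpoint needs a window that covers the period at risk without holes. Section 6.1 provides two labels, acute and late, but the first opens only after SBRT and the second only after the first has closed. The course itself belongs to neither. That is when the intervention is being delivered, and section 7.2(b) places acute effects partly there.

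At stake is the reported Grade 2+ acute rate. If the tabulation follows 6.1 literally, a patient whose only Grade 2+ event came and went during the course does not appear in the acute rate, and does not appear among late events either. If the tabulation follows the sense of 7.2(b), the same patient counts. The same data can thus give two primary results, and the plan does not say which is meant.

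**Working it through.** **Inputs.** Course of 5-7 days (section 4.3.1a). Surgery at most 21 days after completion (section 4.3.3). Twelve evaluable patients (sections 3.1 and 9). The documents give no expected Grade 2+ rate, event timing, threshold or test, so there is no figure of the plan's own to reproduce. Section 7.1(b) describes the course as lasting 1-2 weeks. That should be reconciled with 4.3.1a, but the steps below hold for either length.

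**Step 1: what post SBRT means.** Section 6.3 says "any toxicity leading to radiation treatment break and delay in surgical resection beyond 3 weeks post SBRT will be noted". Section 4.3.3 gives the same 3-week limit in full: "Surgery will be performed no more than 3 weeks after completion of radiation therapy". Read together, post SBRT is counted from completion, not from the first fraction.

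**Step 2: classify events under 6.1.**

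- Begins and resolves during the course: before the window, so not acute; not after the window, so not late. Unclassified.
- Begins during the course and is still present after the last fraction: 6.1 says occur, not start. By onset it is unclassified; by presence it can be acute. Ambiguous.
- Begins after completion, before resection and inside the 4-week limit: acute, subject to how the 1 in 1-4 weeks is read.
- Begins after that: late.

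**Step 3: compare with the rest of the protocol.** Section 7.2(b) counts effects during treatment as acute, which is a direct conflict with the first line of Step 2. Sections 6.2 and 6.5 show that on-treatment toxicity is foreseen and assessed, but they do not say how it is to be labelled. They fit 7.2(b) without contradicting 6.1.

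**Step 4: direction.** Keep the end of the window fixed (resection or 4 weeks, whichever is first). Let A be the patients with a Grade 2+ TRAE counted by 6.1, and B those with one at any time from the first fraction to the same end. Every patient in A is in B, whether onset or presence is used. With the same denominator, A/n is at most B/n. The two are equal if no patient has Grade 2+ events solely in the gap.

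**Step 5: size.** With g patients whose only Grade 2+ event falls in the gap, and n = 12:

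- Reported rate = (B - g)/12, so each such patient costs 1/12 = 8.3 percentage points.
- Illustration with an assumed B = 4: g = 0 gives 4/12 = 33.3%; g = 1 gives 3/12 = 25.0%; g = 2 gives 2/12 = 16.7%.

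B and g are assumptions; the documents support no particular value of either.

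**Step 6: share of time.** If surgery falls at the limit, first fraction to resection spans 5 + 21 = 26 to 7 + 21 = 28 days. A window opening at completion covers 21/26 = 81% to 21/28 = 75%. The course is the remaining 19-25% of the days. This is a share of time, not of events.

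**The case against.** The strongest reply is that this is a drafting slip with little consequence. Section 7.2(b) makes the intent fairly plain. Section 6.3 records onset, resolution and duration for every event, so a correct table can be made at analysis. The stopping rules in sections 6.5 and 9 do not use the acute label, and no threshold or test is attached to 2.2(b). The study is small and descriptive, and 6.5 expects the commonest acute effects to be mild, so few Grade 2+ events may be involved. All of this stands. It limits the harm to the reported endpoint, but it does not make 6.1 right: the one section that defines the endpoint gives a different answer from the risk section.

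The reply is also right on reach. A reader might infer more than the text supports:

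- *Every event that starts during SBRT is lost.* Section 6.1 says occur, so an event that persists past the last fraction may still count. That includes a Grade 3 event that stops treatment, if it is still present afterwards. Only events confined to the course are certainly left out.
- *The whole protocol contradicts 6.1.* Only 7.2(b) does so directly. In 6.5 the timing phrase belongs to a sentence on serious events ("We do not anticipate any serious treatment related adverse events will take place during or immediately following SBRT treatment"), and the sentence on expected acute toxicities gives no timing.
- *The first week after SBRT is excluded too.* This needs the strictest reading of 1-4 weeks. The point does not rely on it.

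**Conclusion.** Wrong as written. Section 6.1 leaves Grade 2+ events confined to the SBRT course outside both the acute and the late class, against 7.2(b), and leaves events that straddle the last fraction undecided. For primary objective 2.2(b) the error runs one way: the rate may be understated and cannot be overstated.

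The documents do not support the claim that the rate will be understated, or by how much. The loss is 8.3 percentage points per affected patient, and the number of such patients may be zero. That step rests on taking the 12 evaluable patients as the denominator, as section 9 suggests without stating it outright. The direction rests only on post SBRT meaning after completion, which sections 6.3 and 4.3.3 establish between them.

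This is worth correcting before the data are tabulated, so that the definition is not chosen with the results in view.

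**What to change.** Reword section 6.1 so that both classes are defined by onset date and meet without a gap:

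- Acute TRAE: onset from the first SBRT fraction until surgical resection or 4 weeks after the last fraction, whichever comes first.
- Late TRAE: any onset after that.

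This keeps the resection limit and the 4-week limit already in 6.1. It moves only the start of the window and settles the onset-or-presence question. Surgical morbidity stays under objective 2.2(c). Section 6.1 should be checked against 7.2(b) so that the two agree.

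The cost is a short amendment. No new visit or data item is needed: 6.2 already assesses patients during radiation, 6.3 already records onset dates, and the end of the window is unchanged. The downside for the sponsor is that the reported acute rate may be higher than under the present wording.
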